6.0 Radiation Therapy

6.1 Localization, Simulation and Immobilization

- 6.1.1 Treatment in the prone position is preferred. Treatment in the supine position will be allowed if the patient cannot tolerate that position, or the breast size is not suitable for prone RT as determined by the treating radiation oncologist.
- 6.1.2 Patients should be optimally positioned with alpha cradle casts and breast boards. Note that all immobilization devices must be MRI compatible
- 6.1.3 Methods to minimize cardiac exposure and target volume motion such as gating and deep-inspiration breath hold are allowed
- 6.1.4 A treatment planning CT scan in the treatment position will be required to define target volumes and for beam modeling. Dual-Energy CT will also be performed to enhance target delineation.
 - 6.1.4.1 Radio-opaque markers may be placed on external landmarks at the acquisition of the CT scan to facilitate contouring segmentation of the CT data-set.
 - 6.1.4.2 The CT should extend cephalad to the mandible and extend sufficiently caudally to encompass the entirety of the breast tissue and the lung volume.
 - 6.1.4.3 A CT scan image thickness of 5mm or less should be used
- 6.1.5 External skin localization marks which may include permanent tattoos are recommended for daily localization and set-up accuracy.
- 6.1.6 MRI simulation will also be performed in the treatment position and same immobilization device created during the CT simulation.
- 6.1.7 MRI simulation will be performed on the 3.0T large bore MRI unit (MAGNETOM Verio, Siemens) with gadolinium contrast per Froedtert Hospital guidelines and guidelines in the department of radiation oncology.
- 6.1.8 Patients will be scanned with commercially available and custom built RF transmitter/receiver coils.
- 6.1.9 In addition to the standard imaging MR sequences, additional advanced imaging sequences will be obtained:
 - 6.1.9.1 *Diffusion Weighted Imaging (DWI) and Apparent Diffusion Coefficient (ADC) Map.* A DWI sequence of about four minutes duration will be acquired. Sequences will be acquired during free-breathing. For patients scanned in the prone position, these scans will not be gated (it is anticipated that this will be the majority of patients). For patients scanned in the supine position, free breathing will again be used, but the images will be gated. B-values of 0-10000 in 6-25 directions will be used in these scans. B-values of 50, 400 and 800 will be used to derive the ADC map.
 - 6.1.9.2 *Perfusion Weighted Imaging (PWI) Dynamic Contrast-Enhanced (DCE)* will be used for perfusion imaging. A spoiled gradient echo sequence will be executed in repetition for about eight minutes while a contrast agent is administered intravenously to the patient. An FDA approved adult dose (0.05 mmol/kg) of MRI gadolinium contrast agent will be used. This contrast agent injection will be used to define the macroscopic boundaries of the tumor for T1-weighted post-contrast images, which are **the standard of care**. The acquisition of PWI scans will not necessitate any additional amount of contrast agent injection to the patient, because both the standard T1-weighted post-contrast images and the PWI images will be acquired with the same amount of contrast injection. In case the patient will

not be administered contrast agent for the T1-weighted images, as part of the standard simulation, then PWI scans will not be performed for that patient.

6.2 Treatment Planning – Target Volumes and Organs at Risk

6.2.1 The definitions for the CTV, PTV and normal structures used in this protocol generally conform to the RTOG-endorsed consensus guidelines for delineation of target and normal structures for breast cancer.

(<http://www.rtog.org/CoreLab/ContouringAtlases/BreastCancerAtlas.aspx>)

6.2.2 The target volume will be defined by fusing image data sets in the planning system from both CT and MRI scans obtained in the treatment position. Fusion will be performed with preference given to breast alignment.

6.2.3 Target Volumes

6.2.3.1 *Gross Tumor Volume (GTV)* will be defined as all gross tumor extent as seen on the MRI scan.

6.2.3.2 *Clinical Target Volume 1 (CTV1)* will be defined as a 0.5cm expansion around the GTV, limited to 5mm within the skin surface and to normal barriers to tumor spread such as the muscle and bone of the chest wall. This volume is designed to correspond to the tissue that would be removed during a typical lumpectomy.

6.2.3.3 *Clinical Target Volume 2 (CTV2)* will be defined as a 1.0cm expansion around CTV1, again limited to 5mm within the skin surface and to normal barriers to tumor spread such as the muscle and bone of the chest wall. This volume is similar to the lumpectomy to CTV expansion used in most post-operative APBI protocols. This total expansion of 1.5cm (CTV1+CTV2) also correlates with data linking MRI delineation of tumor volume with pathological extent of disease (103).

6.2.3.4 *Planning Target Volume (PTV)* will be an expansion to account for daily set-up uncertainty and motion occurring during treatment. If daily kilovoltage CT imaging is used for image guidance treatment delivery, a PTV expansion of 0.3 cm will be used. A PTV of 0.5 cm will be used if daily megavoltage CT imaging is used. The PTV should not be limited inside the skin or at the chest wall. This volume will be used for aperture generation, but not for analysis of the dose volume histogram.

6.2.3.5 *Planning Target Volume Eval (PTV_Eval)* will be based on the PTV, but limited to 0.5cm within the skin. It may extend in to the muscle of the chestwall, but should not extend deep/posteriorly to the anterior surface of the ribs.

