6.2.4 Normal Structures

6.2.4.1 *Breast volume* – Includes the apparent glandular breast tissue as defined on CT and MRI. Consensus anatomical borders as defined in the RTOG atlas should be used. The breast is limited anteriorly within 0.5cm from the skin and posteriorly to the anterior surface of the pectoralis and serratus anterior muscles and should exclude the chest wall.

6.2.4.2 *Contralateral Breast* – Includes the apparent glandular breast tissue as defined on CT and MRI. Given the fusion alignment based on the ipsilateral breast, MRI data may be less useful in defining this volume. Otherwise, the contralateral breast will be defined similarly to the ipsilateral breast as described above.

6.2.4.3 *Ipsilateral Lung* – may be contoured with auto-segmentation with manual verification

- 6.2.4.4 Contralateral Lung – may be contoured with auto-segmentation with manual verification
- 6.2.4.5 Heart – This is to be contoured in all cases, not just left sided cases. The heart should be contoured beginning just inferior to the level in which the pulmonary trunk branches into the left and right pulmonary arteries (PA). Above the PA, none of the heart's 4 chambers are present and no contours should appear above that level. The heart should be contoured inferiorly on every slice inferior to that until its inferior extent near the diaphragm. It is not necessary to include pericardial fat in the heart contour.
- 6.2.4.6 Thyroid – all lobes of the thyroid should be contoured

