6.3 Treatment Planning – Plan Generation

- 6.3.1 3D conformal radiation therapy (3DCRT) or intensity modulated radiation therapy (IMRT) will be allowed. If 3D planning is used, dose will be delivered through at least 3 beams.
- 6.3.2 The PTV (not PTV_Eval) will be used for aperture generation
- 6.3.3 The dose prescription will be consistent with recently reported phase III study of APBI delivered in the post-operative setting. Patients will receive 30Gy in 5 fractions of 6Gy, given on non-consecutive days (95). Total treatment duration should be no longer than 18 days.
- 6.3.4 Skin bolus is not allowed

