6.4 Treatment Planning – Dose Constraints

- 6.4.1 PTV
 - 6.4.1.1 *Ideal* – 95% of the PTV will be covered by the prescription dose of 30Gy
Acceptable Variation – 95% of the PTV will be covered by 95% of the prescription dose
- 6.4.2 Breast Volume
 - 6.4.2.1 *Ideal* – Less than 25% of the total breast volume should receive the prescription dose of 30Gy
Acceptable Variation – Less than 35% of the total breast volume should receive the prescription dose of 30Gy
 - 6.4.2.2 *Ideal* – Less than 45% of the total breast volume should receive 50% of the prescription dose (15Gy)
Acceptable Variation – Less than 50% of the total breast volume should receive 50% of the prescription dose (15Gy)

Note: Failure to meet the above constraints may constitute a patient who is not a candidate for APBI. If both these constraints are not met, the patient should be taken off study and treated per standard of care.

- 6.4.2.3 *Ideal* – Max dose within the breast should be less than 108% of the prescription dose (32.4Gy)
Acceptable Variation – Max dose within the breast should be less than 110% of the prescription dose (33Gy)
- 6.4.3 Contralateral Breast
 - 6.4.3.1 *Ideal* – Less than 5% of the contralateral breast should receive 5% of the prescription dose (1.5Gy).
Acceptable Variation – Less than 5% of contralateral breast should receive 8% of the prescription dose (2.4Gy).

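### Section 6.4.1 sets the only target-coverage limit on the PTV, which 6.2.3.4 excludes from dose-volume analysis; PTV_Eval, defined next, has no limit in 6.4

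*Combined protocol and SAP*

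**What the plan says.** Section 6.2.3.4 defines the PTV as the set-up and motion expansion: 0.3 cm with daily kilovoltage CT guidance, 0.5 cm with megavoltage CT. It adds "The PTV should not be limited inside the skin or at the chest wall" and, on its use, "This volume will be used for aperture generation, but not for analysis of the dose volume histogram".

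Section 6.2.3.5 then defines PTV_Eval, which "will be based on the PTV, but limited to 0.5cm within the skin" and, on the deep side, "should not extend deep/posteriorly to the anterior surface of the ribs". Section 6.3.2 keeps the two names apart: "The PTV (not PTV_Eval) will be used for aperture generation".

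Section 6.4.1, headed PTV, sets coverage. The ideal is "95% of the PTV will be covered by the prescription dose of 30Gy"; the acceptable variation is "95% of the PTV will be covered by 95% of the prescription dose". The rest of 6.4 covers the ipsilateral and contralateral breast, both lungs and the heart. PTV_Eval, GTV, CTV1 and CTV2 do not appear there.

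Two further provisions bear on the consequence. Section 6.3.4 bars skin bolus. Section 6.2.4.1 says of the breast contour: "The breast is limited anteriorly within 0.5cm from the skin".

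**The concern.** A requirement that 95% of a volume receive a given dose is a dose-volume criterion and is checked on the dose-volume histogram. Section 6.4.1 thus asks for a reading that 6.2.3.4 says is not to be made on that structure, while the structure whose name marks it for evaluation is given no task. A planner can follow 6.4.1 literally or follow 6.2.3.4, and may reach different answers on the same plan.

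The difference lies in the 5 mm under the skin. PTV_Eval leaves that layer out; the PTV may enter it. On a literal reading, a plan giving full dose to all of PTV_Eval can miss 6.4.1 unless part of that layer is also brought to 30 Gy (28.5 Gy for the acceptable variation), without bolus. No limit in 6.4 restrains dose there: the breast contour stops short of the layer, so the volume and maximum-dose limits of 6.4.2 do not count it, and 6.4 has no skin limit. What is at stake is consistent plan acceptance for shallow tumors.

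**Working it through.** **Stated doses.** 5 × 6 Gy = 30 Gy, and 0.95 × 30 = 28.5 Gy. The plan gives no figure for the difference between the PTV and PTV_Eval, so there is none to reproduce.

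**Inputs from the protocol.** CTV1 = GTV + 5 mm and CTV2 = CTV1 + 10 mm, each kept 5 mm inside the skin (6.2.3.2, 6.2.3.3). PTV margin m = 3 or 5 mm, untrimmed (6.2.3.4). PTV_Eval = PTV trimmed 5 mm inside the skin (6.2.3.5). Tumor size up to 3.0 cm (3.1.3).

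**Assumptions.** Spherical GTV, flat skin, chest wall ignored, and PTV grown from CTV2 (6.2.3.4 does not name the base volume). The documents give no tumor depths, so depth is varied.

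**Step 1: where the edges lie.** With the near edge of the GTV at depth g, the untrimmed edge of CTV2 is at g − 15 mm. For g from 5 to 20 mm this is 5 mm or less, so trimming puts it at 5 mm. The PTV edge is then at 5 − 3 = 2 mm, or 5 − 5 = 0 mm (the skin). PTV_Eval stops at 5 mm.

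**Step 2: share of the PTV outside PTV_Eval.** s = volume of PTV shallower than 5 mm ÷ total PTV volume, by numerical integration on a 0.1 mm grid:

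| Near edge depth | Margin | 10 mm tumor | 20 mm tumor | 30 mm tumor |
|---|---|---|---|---|
| 5 mm | 0.3 cm | 11.6% | 8.0% | 5.8% |
| 5 mm | 0.5 cm | 16.7% | 11.9% | 8.9% |
| 10 mm | 0.3 cm | 8.2% | 5.7% | 4.1% |
| 10 mm | 0.5 cm | 12.2% | 8.8% | 6.6% |
| 15 mm | 0.3 cm | 4.8% | 3.3% | 2.4% |
| 15 mm | 0.5 cm | 7.7% | 5.5% | 4.1% |

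At 20 mm depth the share is about 1% (0.3 cm) or at most about 3% (0.5 cm).

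**Step 3: when the result can change.** With PTV_Eval fully covered and nothing shallower at dose, coverage of the PTV is 1 − s, so 6.4.1 is missed when s > 5%. For 10, 20 and 30 mm tumors this holds from 5 mm depth down to about 15, 11 and 7 mm (0.3 cm margin) or 18, 16 and 13 mm (0.5 cm margin).

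**Step 4: how much more must be covered.** The share of the outer layer that must reach dose is (s − 0.05)/s. For the 20 mm tumor 5 mm deep: (0.0796 − 0.05)/0.0796 = 37%, or (0.1192 − 0.05)/0.1192 = 58%. If coverage extends evenly toward the skin from the 5 mm plane, the extra reach for 10, 20 and 30 mm tumors is:

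- 0.3 cm margin: about 1.7, 1.1 and 0.4 mm at 5 mm depth; 1.1, 0.4 and 0 mm at 10 mm; none at 15 mm.
- 0.5 cm margin: about 3.4, 2.8 and 2.1 mm at 5 mm depth; 1.5, 0.4 and 0 mm at 15 mm.

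**Step 5: what the change of structure would leave out.** For a GTV whose edge is 2 mm deep, the part shallower than 5 mm is a spherical cap of height h = 5 − 2 = 3 mm. Its share is [πh²(3R − h)/3] ÷ [4πR³/3]:

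- R = 5 mm: 36 ÷ 166.7 = 21.6%
- R = 10 mm: 81 ÷ 1333.3 = 6.1%
- R = 15 mm: 126 ÷ 4500 = 2.8%

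**The case against.** The strongest reply is that the text nearly resolves itself. A planner told that the PTV is not for dose-volume analysis, and then given a structure named for evaluation, will probably read 6.4.1 on PTV_Eval. That is the likely intent, and it makes this a drafting slip. It does not remove the point: the documents never say in words that PTV_Eval is the evaluation structure, and 6.3.2 shows that the authors use the two names for different things.

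The second reply is that the gap is small in distance. This stands. With the 0.3 cm margin the extra reach is under 2 mm even at 5 mm depth, where 6.1.4.3 allows CT slices up to 5 mm thick. The larger gap arises only with the 0.5 cm margin, tied to megavoltage CT.

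A reader might also infer more than the documents support:

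- **That a miss takes a patient off study.** Section 6.4.1 states no consequence. The off-study note belongs to the breast-volume limits in 6.4.2.
- **That tumors would be underdosed or complications increased.** Nothing in the documents shows either.
- **That the chest-wall side adds a comparable problem.** PTV_Eval may extend into the chest-wall muscle. For a tumor touching the muscle, the difference vanishes once the muscle over the rib is at least as thick as the margin (3 or 5 mm). The documents give no thickness.
- **That objective 2.2.6 should be tied to PTV_Eval.** The earlier protocol's coverage structure is not in the documents, so this could create a mismatch. Both volumes are defined here, and either can be extracted later.

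**Conclusion.** The inconsistency is real and is wrong as written: an operative planning rule names a structure that the protocol sets aside from that use. Its practical size is modest and confined to shallow tumors. In the reference case, a 20 mm tumor 5 mm deep, it amounts to about 1 mm (0.3 cm margin) or 3 mm (0.5 cm margin) of extra isodose reach. By about 20 mm depth, full coverage of PTV_Eval satisfies 6.4.1 on either structure. These sizes depend on the idealized geometry stated above. Without tumor depths, the number of patients affected cannot be estimated. The primary endpoint counts patients with post-operative complications, and the two-stage design in 11.1 does not use the coverage rule, so endpoint, sample size and error rates are untouched. This is a correction worth considering, not a threat to the trial's conclusions.

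**What to change.** In the heading and both lines of 6.4.1, replace PTV with PTV_Eval. Leave the aperture rule in 6.3.2 and objective 2.2.6 as they are. For tumors within 5 mm of the skin, also report GTV coverage, because PTV_Eval can leave out part of the GTV: about 22%, 6% and 3% for 10, 20 and 30 mm tumors with an edge 2 mm deep.

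The cost is one term in three places and one added reporting line for a subset of patients. No new contour, procedure, visit or patient is needed, and apertures are still drawn on the PTV. The trade-off is that GTV shallower than 5 mm would no longer count toward 6.4.1; the added report keeps it visible.

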6.2.4 Normal Structures

6.2.4.1 *Breast volume* – Includes the apparent glandular breast tissue as defined on CT and MRI. Consensus anatomical borders as defined in the RTOG atlas should be used. The breast is limited anteriorly within 0.5cm from the skin and posteriorly to the anterior surface of the pectoralis and serratus anterior muscles and should exclude the chest wall.

6.2.4.2 *Contralateral Breast* – Includes the apparent glandular breast tissue as defined on CT and MRI. Given the fusion alignment based on the ipsilateral breast, MRI data may be less useful in defining this volume. Otherwise, the contralateral breast will be defined similarly to the ipsilateral breast as described above.

6.2.4.3 *Ipsilateral Lung* – may be contoured with auto-segmentation with manual verification

- 6.2.4.4 Contralateral Lung – may be contoured with auto-segmentation with manual verification
- 6.2.4.5 Heart – This is to be contoured in all cases, not just left sided cases. The heart should be contoured beginning just inferior to the level in which the pulmonary trunk branches into the left and right pulmonary arteries (PA). Above the PA, none of the heart's 4 chambers are present and no contours should appear above that level. The heart should be contoured inferiorly on every slice inferior to that until its inferior extent near the diaphragm. It is not necessary to include pericardial fat in the heart contour.
- 6.2.4.6 Thyroid – all lobes of the thyroid should be contoured

6.3 Treatment Planning – Plan Generation

- 6.3.1 3D conformal radiation therapy (3DCRT) or intensity modulated radiation therapy (IMRT) will be allowed. If 3D planning is used, dose will be delivered through at least 3 beams.
- 6.3.2 The PTV (not PTV_Eval) will be used for aperture generation
- 6.3.3 The dose prescription will be consistent with recently reported phase III study of APBI delivered in the post-operative setting. Patients will receive 30Gy in 5 fractions of 6Gy, given on non-consecutive days (95). Total treatment duration should be no longer than 18 days.
- 6.3.4 Skin bolus is not allowed

6.4 Treatment Planning – Dose Constraints

- 6.4.1 PTV
 - 6.4.1.1 *Ideal* – 95% of the PTV will be covered by the prescription dose of 30Gy
Acceptable Variation – 95% of the PTV will be covered by 95% of the prescription dose
- 6.4.2 Breast Volume
 - 6.4.2.1 *Ideal* – Less than 25% of the total breast volume should receive the prescription dose of 30Gy
Acceptable Variation – Less than 35% of the total breast volume should receive the prescription dose of 30Gy
 - 6.4.2.2 *Ideal* – Less than 45% of the total breast volume should receive 50% of the prescription dose (15Gy)
Acceptable Variation – Less than 50% of the total breast volume should receive 50% of the prescription dose (15Gy)

Note: Failure to meet the above constraints may constitute a patient who is not a candidate for APBI. If both these constraints are not met, the patient should be taken off study and treated per standard of care.

- 6.4.2.3 *Ideal* – Max dose within the breast should be less than 108% of the prescription dose (32.4Gy)
Acceptable Variation – Max dose within the breast should be less than 110% of the prescription dose (33Gy)
- 6.4.3 Contralateral Breast
 - 6.4.3.1 *Ideal* – Less than 5% of the contralateral breast should receive 5% of the prescription dose (1.5Gy).
Acceptable Variation – Less than 5% of contralateral breast should receive 8% of the prescription dose (2.4Gy).

6.4.4 Ipsilateral Lung

- 6.4.4.1 *Ideal* – Less than 10% of the ipsilateral lung should receive 30% of the prescription dose (9Gy).
Acceptable Variation – Less than 15% of the ipsilateral lung should receive 30% of the prescription dose (9Gy).
- 6.4.4.2 *Ideal* – Less than 30% of the ipsilateral lung should receive 10% of the prescription dose (3Gy).
Acceptable Variation – Less than 35% of the ipsilateral lung should receive 10% of the prescription dose (3Gy).

6.4.5 Contralateral Lung

- 6.4.5.1 *Ideal* – Less than 10% of the contralateral lung should receive 10% of the prescription dose (3Gy).
Acceptable Variation – Less than 15% of the contralateral lung should receive 10% of the prescription dose (3Gy).

6.4.6 Heart

- 6.4.6.1 For Left Sided Cases: *Ideal* – Less than 10% of heart should receive 5% of the prescription dose (1.5Gy).
Acceptable Variation – Less than 10% of the heart should receive 8% of the prescription dose (2.4Gy).
Ideal – Mean heart dose should not exceed 200cGy
Acceptable Variation – Mean heart dose should not exceed 320cGy
- 6.4.6.2 For Right Sided Cases: *Ideal* – Less than 5% of heart should receive 5% of the prescription dose (1.5Gy).
Acceptable Variation – Less than 5% of the heart should receive 8% of the prescription dose (2.4Gy).
Ideal – Mean heart dose should not exceed 200cGy
Acceptable Variation – Mean heart dose should not exceed 320cGy

6.5 Radiation Treatment Delivery

- 6.5.1 Treatment should generally begin within 60 days of enrollment. At least one day will elapse between each fraction so that treatments are not delivered on consecutive days.
- 6.5.2 A pair of orthogonal portal images will be obtained at time of the second simulation and will be reviewed by a radiation oncologist prior to the first treatment.
- 6.5.3 Daily CT or MRI-based image guided radiotherapy will be used for table shifts and field placement at the time of second simulation and with each treatment fraction. Alignment to the biopsy clip, breast position, and tumor if visible on CT/MRI will be used.
- 6.5.4 On-line adaptive replanning will be allowed for patients treated with daily kilovoltage-CT or MRI based image guided radiotherapy.
- 6.5.5 Treatment should ideally be given over no more than 14 elapsed days, but up to 18 days will be allowed. Extenuating circumstances (e.g. patient unable to come for treatment, prolonged down-time on treatment machine) resulting in treatment interruption will be clearly documented.
- 6.5.6 Patients will be seen once during the treatment course for weekly review as per standard protocols in the radiation oncology department. Ideally, one of those visits should occur on the last day of treatment. Breast exam during that visit and documentation of skin reactions will be documented.

7.0 Systemic Therapy

7.1 Chemotherapy

Chemotherapy may be given and chemotherapeutic agents used are at the discretion of the patient's medical oncologist. The use of chemotherapeutic agents before or during radiation therapy is not allowed and is permitted only as an adjuvant to surgery as is the current standard for patients treated with post-operative APBI.

For the patient population for this study, resected tumor specimens often are tested with a commercially available quantitative reverse transcriptase polymerase chain reaction (RT-PCR) analysis of 21 individual genes. The results of this assay are then used to develop a recurrence score to guide decisions regarding systemic chemotherapy (OncotypeDx). Because this test is usually performed on the final surgical specimen, there is concern that any tumor regression occurring as a result of pre-operative radiation therapy might lead to a loss of important information that can guide treatment decisions. However, if there is adequate tumor present in the core biopsy used to diagnose breast cancer, the 21-gene assay may be performed on the biopsy specimen instead of the final surgical specimen. Furthermore, data presented at the San Antonio Breast Cancer Symposium in 2011 demonstrated 92% concordance between Oncotype performed on core biopsies and surgical specimens (93). This level of concordance is comparable to that of negative sentinel lymph node biopsy predicting no axillary lymph node involvement. In a recent analysis of the 548 reportable Oncotype DX tests performed at Froedtert Hospital from 2010-mid 2015, only 9% had a high recurrence score (Data from Oncotype reporting, prepared by [name]). Furthermore, the patients on this protocol are generally considered low risk for a high Oncotype Score.

Included in the eligibility criteria for this protocol is that the biopsy specimen contain adequate tissue to perform the OncotypeDx assay. The high concordance of biopsy OncotypeDx score with final surgical specimens coupled with the very low probability of a high Oncotype recurrence score in this patient population make it extremely unlikely that a patient with a high score will somehow be missed and hence not receive systemic chemotherapy as a result of receiving pre-operative radiation therapy.

